3.5 Estimands

The primary and key secondary estimands are described in Table 1 below. The analyses will be performed on the Full Analysis Set (FAS) as defined in [Section 8](#). Other Secondary and Exploratory efficacy endpoints (specified in [Sections 16.3](#) and [16.4](#)) will generally be subject to the population, intercurrent event handling strategy, and population-level summary measures similar to the primary estimand. Supplementary analyses for the primary and key secondary

estimands will be performed using the FAS, Modified Full Analysis Set (mFAS), and Per Protocol (PP) populations.

Intercurrent events include exposure to rescue therapy for UC – see [Section 25](#), Appendix IV for the list of rescue therapies applying to this study. Additional intercurrent events include missed endoscopy at Visit 7 Week 13 for participants available to have a Visit 7 Week 13 endoscopy, and study discontinuation for either disease worsening or treatment-emergent adverse event with a preferred term indicating ulcerative colitis. See [Sections 16](#), [16.1.2](#), and [29](#) (Appendix VIII).

Participants will be evaluated for exposure to rescue therapy by Ventyx reviewers according to the guidelines presented in [Section 25](#), Appendix IV. Participants deemed to have received rescue therapy, and not experiencing other deviations preventing contribution to the primary and key secondary analyses of the primary and key secondary efficacy endpoints, will be treated as non-responders in those analyses; they will also be included in the Per Protocol analysis set. Use of concomitant medications and procedures that are not potentially effective for the treatment of UC will not be considered intercurrent events.

Table 1. List of Primary and Key Secondary Estimands

Estimand	Definition	Attributes			
		Population	Variable / Endpoint	Primary Intercurrent Event Handling Strategy	Population-Level Summary Measure
Primary Estimand	Efficacy of VTX002 on Clinical Remission (Modified Mayo Score) at Week 13	FAS	Proportion of participants with stool frequency (SF) subscore = 0 or 1, rectal bleeding (RB) subscore = 0, and endoscopic subscore (ES) \leq 1 (excluding friability)	Participants with any intercurrent events prior to Week 13 efficacy assessment will be treated as non-responders	Difference between VTX002 and Placebo with respect to population proportion of clinical remission at Week 13

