Key Secondary Estimand 1	Efficacy of VTX002 on Endoscopic Improvement at Week 13	FAS	Proportion of participants with ES \leq 1 (excluding friability)	Same as the intercurrent event strategy for the primary estimand	Difference between VTX002 and Placebo with respect to population proportion of endoscopic improvement at Week 13
Key Secondary Estimand 2	Efficacy of VTX002 on Symptomatic Remission at Week 13	FAS	Proportion of participants with SF subscore = 0 or 1 and RB subscore = 0	Same as the intercurrent event strategy for the primary estimand	Difference between VTX002 and Placebo with respect to population proportion of symptomatic remission at Week 13
Key Secondary Estimand 3	Efficacy of VTX002 on Histologic Remission at Week 13	FAS	Proportion of participants with Geboes Index score < 2.0	Same as the intercurrent event strategy for the primary estimand	Difference between VTX002 and Placebo with respect to population proportion of histologic remission at Week 13
Key Secondary Estimand 4	Efficacy of VTX002 on Endoscopic Improvement-Histologic Remission at Week 13	FAS	Proportion of participants with ES \leq 1 (excluding friability) and Geboes Index score < 2.0	Same as the intercurrent event strategy for the primary estimand	Difference between VTX002 and Placebo with respect to population proportion of mucosal healing at Week 13

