16. EFFICACY

Controlled efficacy analyses are limited to the Induction Treatment Period. Efficacy endpoints may be computed for LTE and OLE study visits, but all hypothesis testing will be uncontrolled, resulting in nominal p-values and CIs only.

The study is designed to show superiority of VTX002 60 mg to placebo for the primary efficacy endpoint at Induction Week 13. Four key secondary endpoints are defined for this study and VTX002 30 mg is an important additional active drug dose of interest. Across the primary endpoint and key secondary endpoints, a total of ten (10) Induction Week 13 controlled hypothesis tests involving the two randomized VTX002 doses and placebo are planned. The family-wise error rate will be maintained at $\alpha = 0.05$ – see [Section 10.3](#) for details.

All controlled efficacy analyses (Week 13, Induction) will be primarily based on participant stratum at randomization (see [Section 10.2](#)) according to IWRS and for the FAS. Participants having MMS = 4 at baseline will be excluded from all efficacy analyses except the sensitivity analysis described in [Section 16.1.5](#). Additional sensitivity and/or supportive analyses will be performed as described elsewhere in this section. For composite scores such as MMS, if one or more components is missing from an analysis visit window the composite score is missing.

Blinded study team review will be used prior to Induction interim database lock and unblinding, to attribute a known Induction Week 13 non-response to participants having specific on-study experiences. Participants will be classified as non-responders in all responder-based efficacy analyses, including the primary endpoint, at all timepoints subsequent to the experience of the earliest of any of the following intercurrent events:

- Missed Visit 7 Week 13 endoscopy for participants eligible to have Visit 7 Week 13 endoscopy
- Discontinuation of the study during the Induction Treatment Period for either disease worsening or treatment-emergent adverse event having a preferred term indicating ulcerative colitis (UC)

- Exposure to rescue therapy for UC. See Appendix IV, [Section 25](#).

For a given participant, if efficacy outcomes (as opposed to components of outcomes) are available subsequent to an intercurrent event, they will be flagged as such. Participants may be included in the PP Set as long as other Per Protocol criteria are not violated.

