16.1.2 Missing Data Methods for the Primary Efficacy Variable

The concept of non-response for participants with non-missing Week 13 Induction primary efficacy outcomes is described at the beginning of [Section 16](#). For participants with missing Week 13 Induction Treatment Period primary efficacy outcomes, the following missing data methods will be used:

- Primary method: single imputation as non-responder
- Sensitivity analyses
 - multiple imputation under missing at random (MAR)
 - multiple imputation with Copy Reference (CR) under missing not at random (MNAR)
 - tipping point analysis
- Supplementary analyses: mFAS and PP set analysis with data as observed

These methods are discussed in more detail below. See [Section 29](#) (Appendix VIII) for a tabular presentation of the relationship between intercurrent events, missing data, and response imputation.

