28. APPENDIX VII. DETERMINATION OF SAMPLE SIZE

Based on literature data review, the expected proportion of clinical remission at Induction Week 13 is 28% for VTX002 60 mg and 8% for placebo (Sandborn 2016; Sandborn 2020). Under these assumptions, and with a 1:1 randomization ratio, 2-group chi-squared test, and two-sided significance level of 5%, a sample of 57 participants per treatment group will be sufficient to achieve at least 80% power. Adding a 10% inflation for dropouts results in 63 participants per treatment group and 189 participants in total.

Software

SAS (version 9.4; SAS Institute Inc.; Cary, NC, USA).

Input & Output

Fixed Scenario Elements	
Distribution	Asymptotic normal
Method	Normal approximation
Number of Sides	2
Alpha	0.05
Group 1 Proportion	0.08
Group 2 Proportion	0.28
Nominal Power	0.8
Null Proportion Difference	0

Computed N per Group	
Actual Power	N per Group
0.802	57

29. APPENDIX VIII. RELATIONSHIP OF INTERCURRENT EVENTS TO NON-RESPONDER IMPUTATION, MULTIPLE IMPUTATION, COPY REFERENCE IMPUTATION, AND TIPPING POINT

Table 12. Relationships Between Various Types of Imputation and Data Missingness

Type of Occurrence	Visits Affected	Effect of Protocol Deviations	Primary Analysis of Primary, Key Secondary, and Other Secondary Endpoints	Multiple Imputation	Copy Reference	Tipping Point
Intercurrent Event	All visits on/after intercurrent event, regardless of data missingness for other reasons . Intercurrent event handling takes priority over missing data handling.	An intercurrent event is a major protocol deviation. As long as other deviations don't prevent the participant from being Per Protocol, they will be included in the PP Set.	Non-responder imputation	Non-responder imputation	Non-responder imputation	Non-responder imputation
Missing Data	Visits w/ efficacy endpoints having missing values in one or more endpoint components.	As long as there are no intercurrent events, missing data is handled per this row in the table.	Non-responder imputation	Multiple imputation	Copy reference imputation	Tipping point imputation

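### A missed Week 13 endoscopy is locked at non-response as an intercurrent event, contradicting the tipping-point text, leaving it untested under Table 12, and allowing an observed symptomatic remission to be overwritten

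*SAP*

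**What the plan says.** SAP 16 lists as an intercurrent event "Missed Visit 7 Week 13 endoscopy for participants eligible to have Visit 7 Week 13 endoscopy". SAP 3.5 has the same event with a different qualifier: "Additional intercurrent events include missed endoscopy at Visit 7 Week 13 for participants available to have a Visit 7 Week 13 endoscopy". Neither eligible nor available is defined.

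Table 1 sets the primary strategy: "Participants with any intercurrent events prior to Week 13 efficacy assessment will be treated as non-responders". For symptomatic remission, and for the other key secondary estimands, it says "Same as the intercurrent event strategy for the primary estimand".

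Table 12 in Appendix VIII assigns non-responder imputation to intercurrent events in the primary, multiple-imputation, copy-reference and tipping-point columns. It covers "All visits on/after intercurrent event" and adds "Intercurrent event handling takes priority over missing data handling". Its missing-data row applies only on this condition: "As long as there are no intercurrent events, missing data is handled per this row in the table".

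The analysis sections read differently:

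- **16.1.2** ties the Section 16 non-response rule to participants whose Week 13 primary outcome is not missing, and sends missing outcomes to the missing-data methods. It also points to Appendix VIII "for a tabular presentation of the relationship between intercurrent events, missing data, and response imputation".
- **16.1.4.1**, Step 2, reclassifies each imputed dataset by the Section 16 criteria. Copy reference (16.1.4.2) reuses that step.
- **16.1.4.3** simulates a response for every participant without observed RB, SF and ES at Week 13. It reuses Steps 3 and 4 of 16.1.4.1 but not Step 2.
- **16.2** picks the tipping-point set for each key secondary endpoint only by whether that endpoint's data are absent.
- **Appendix II** requires only RB and SF for symptomatic remission. Table 3 footnote c computes both when no endoscopy is associated with the visit.

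**The concern.** A missed endoscopy is a missing endpoint component. Calling it an intercurrent event moves it out of reach of the analyses meant to test assumptions about missing components. Four problems follow.

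1. **Tipping point.** 16.1.4.3 and 16.2 include these participants; Table 12 locks them. A map built under Table 12 can fail to tip because the cases were fixed, not because the result is robust to them.
2. **Multiple imputation and copy reference.** These can be read as agreeing with Table 12 through Step 2, although 16.1.2 restricts the Section 16 rule to non-missing outcomes. On the Table 12 reading, nothing in the missing-data sensitivity set varies missed endoscopies.
3. **Symptomatic remission.** A participant with scorable RB and SF at Week 13 who meets the definition can be counted as a failure because a procedure the endpoint does not use was missed. The timing words conflict: *prior to* in Table 1, *subsequent to* in Section 16, *on/after* in Table 12. Only the last clearly reaches the same visit.
4. **Per Protocol set.** SAP 8 requires membership of the clinical-remission mFAS, which these participants cannot have without an in-window endoscopy. It also says that participants with intercurrent events will be included; Section 16 says only that they may be.

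Symptomatic remission sits in controlled Family 2, so its result affects how much alpha reaches Family 3.

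**Working it through.** **The plan's own figures.** SAP 6 and Appendix VII give 28% v 8%, two-sided 5%, 57 per arm, power 0.802. With the pooled-variance normal approximation,

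n = [1.96 x sqrt(2 x 0.18 x 0.82) + 0.842 x sqrt(0.08 x 0.92 + 0.28 x 0.72)]^2 / 0.20^2 = 56.7, so 57 per arm, with power 0.8019.

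Inflation: 57 x 1.10 = 62.7, so 63. Both reproduce.

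**Tipping-point map, clinical remission.** The documents give no count of missed endoscopies. *Assumed:* 63 per arm; 6 per arm without a Week 13 outcome (57 observed, in line with the 10% dropout figure); observed remitters 0.28 x 57 = 16.0 and 0.08 x 57 = 4.6, taken as 16 v 5.

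Unstratified CMH with N = 126 and 21 responders: (16 - 10.5)^2 / [63^2 x 21 x 105 / (126^2 x 125)] = 30.25 / 4.41 = 6.86, p = 0.009.

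The grid is that of 16.1.4.3: 30 x 30 rates, 0 to 30% by 2 and 35 to 100% by 5. Each CMH value Q is transformed as in SAP Table 5, z = (Q^(1/3) - 7/9) / sqrt(2/9), and pooled with total variance 1 + (1 + 1/40) x B, where B is the between-imputation variance, with a one-sided t p-value. The binomial mean and variance were computed exactly instead of from 40 draws.

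| Varied per arm | Locked per arm | Cells with p >= 0.05 | Lowest tipping placebo rate (active 0%) | Largest p |
|---|---|---|---|---|
| 6 (16.1.4.3 as worded) | 0 | 227 | 40% | 0.279 |
| 5 | 1 | 184 | 45% | 0.185 |
| 4 | 2 | 124 | 60% | 0.115 |
| 3 | 3 | 37 | 80% | 0.067 |
| 2 | 4 | 0 | none | 0.037 |
| 1 | 5 | 0 | none | 0.019 |
| 0 | 6 | 0 | none | 0.009 |

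Plain counts agree. With all six per arm varied and no active responders among them, 2 placebo responders give p = 0.038, 3 give 0.070 and 6 give 0.278 (Pearson, 63 per arm).

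**Symptomatic remission.** Overwriting needs no usable endoscopy in Days 76-108, a site visit in Days 82-102, and enough diary days (Table 3 and SAP 10.3). *Assumed:* 5 to 10% missed, 50 to 100% of those scorable, 20 to 35% of those in remission.

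- Low end: 63 x 0.05 x 0.5 x 0.20 = 0.3 per arm, or 0.5 points.
- High end: 63 x 0.10 x 1.0 x 0.35 = 2.2 per arm, or 3.5 points.

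Starting from an assumed 22 v 11 of 63 (Pearson):

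| Overwritten | Counts | p |
|---|---|---|
| none | 22 v 11 | 0.026 |
| one per arm | 21 v 10 | 0.023 |
| one active only | 21 v 11 | 0.041 |
| two active only | 20 v 11 | 0.063 |
| one placebo only | 22 v 10 | 0.014 |

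**Alpha passed on (SAP 10.4.2, f = 0.7, two hypotheses).** Step 1: 0.7 x 0.05 + 0.3 x 0.025 = 0.0425. Step 2: 0.025. If only one Family 2 hypothesis is rejected, Family 3 receives 0.05 - 0.0425 = 0.0075; if both are, it receives 0.05.

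**The case against.** The SAP has a precedence rule. Table 12 puts intercurrent events first, has its own tipping-point column, and 16.1.2 points to it. On that reading 16.1.4.3 and 16.2 merely omit an exception, and a cross-reference would cure it. Treating a missed endoscopy as failure is prespecified, conservative for the participant's own outcome, and settled in blinded review. The mFAS analysis as observed gives some check.

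The illustrations are also mild. The 10% figure is dropout, whereas the event covers only people still eligible or available at Week 13, so four of six is a strong assumption. Even the 227-cell map tips only at placebo rates of 40% or more, against a planned 8%. In two of the four overwriting examples the p-value falls, and a single active-only overwrite (0.041) still meets the 0.0425 cutoff.

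The points on size stand, and nothing here claims that the primary conclusion is at risk. The precedence argument settles which text wins, but it leaves a missing component varied in no missing-data sensitivity analysis. The clinical-remission mFAS requires ES, so it drops these participants and does not test the non-response assumption. For symptomatic remission the mFAS analysis may keep the observed result, but it is only supplementary, and Section 16 applies non-response to all responder analyses. A cross-reference would not resolve the overwriting.

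**Conclusion.** The concern holds. The tipping-point sections and Table 12 give different instructions for the same participants. If Table 12 is followed, missed Week 13 endoscopies escape every missing-data sensitivity analysis, and an observed result on a type-I-error-controlled endpoint can be replaced by failure.

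The size is unknown because no missed-endoscopy rate is given. On the assumed counts, the tipping map moves from 227 cells to 37 or 0 when three, or four or more, of six missing per arm are locked. For symptomatic remission, 0.3 to 2.2 remitters per arm are exposed, and the between-arm effect can go either way. The primary analyses of clinical remission and of the three endoscopy- or biopsy-based key secondary endpoints do not change, since missing outcomes are already non-response there. What is affected is the robustness evidence, the symptomatic remission result and, through it, possibly the alpha reaching Family 3. This should be fixed before the interim lock.

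**What to change.** 1. Remove missed Week 13 endoscopy from the intercurrent-event lists in SAP 3.5 and 16, so that it falls in Table 12's missing-data row. The primary analysis of endpoints needing ES or Geboes stays non-responder imputation; multiple imputation, copy reference and tipping point then apply as 16.1.4 and 16.2 describe. The Per Protocol conflict and the undefined qualifiers disappear.
2. For the remaining intercurrent events, use one timing phrase in Table 1, Section 16 and Table 12, stating whether the same visit is covered.
3. For Week 13 symptomatic remission and its 16.5 version, in participants with no rescue-therapy or UC-related discontinuation event, use RB and SF from Table 3 footnote b when an endoscopy is associated and footnote c when none is. If either is still missing, use non-response in the primary analysis and Table 12's missing-data methods in the missing-data sensitivity analyses.
4. Sections 16.1.5, 16.1.7 and 16.5 rely on the Section 16 list and otherwise impute nothing. State there that a missed Week 13 endoscopy remains non-response for endpoints needing ES or Geboes.
5. Reconcile footnote c, which computes nothing when there is no site visit, with SAP 10.3, which anchors the look-back to the ideal study day.

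The cost is SAP wording and programming. Each arm's symptomatic remission rate can only stay the same or rise; the difference between arms can move either way.

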16.1 Primary Efficacy

16.1.1 Primary Efficacy Variable and Derivation

Primary efficacy analyses will compare VTX002 60 mg to placebo at Week 13 of the Induction Treatment Period. This will be done for the proportion of participants achieving clinical remission as defined in [Section 7.5](#). Participants who achieve clinical remission will be referred to as responders. Participants who do not achieve clinical remission will be referred to as non-responders.

16.1.2 Missing Data Methods for the Primary Efficacy Variable

The concept of non-response for participants with non-missing Week 13 Induction primary efficacy outcomes is described at the beginning of [Section 16](#). For participants with missing Week 13 Induction Treatment Period primary efficacy outcomes, the following missing data methods will be used:

- Primary method: single imputation as non-responder
- Sensitivity analyses
 - multiple imputation under missing at random (MAR)
 - multiple imputation with Copy Reference (CR) under missing not at random (MNAR)
 - tipping point analysis
- Supplementary analyses: mFAS and PP set analysis with data as observed

These methods are discussed in more detail below. See [Section 29](#) (Appendix VIII) for a tabular presentation of the relationship between intercurrent events, missing data, and response imputation.

16.1.3 Primary Analysis of Primary Efficacy Endpoint

The primary analysis of the primary efficacy endpoint will be completed based on the FAS. The primary endpoint is the proportion of participants with clinical remission at Induction Week 13. The following are the null and alternate hypotheses as stated in the Protocol:

$$H_0: p(\text{VTX002 60 mg}) - p(\text{Placebo}) = 0$$

$$H_A: p(\text{VTX002 60 mg}) - p(\text{Placebo}) \neq 0.$$

For statistical analysis purposes, the following statement will be considered logically equivalent:

$$H_0: p(\text{VTX002 60 mg}) = p(\text{Placebo})$$

$$H_A: p(\text{VTX002 60 mg}) \neq p(\text{Placebo})$$

The null hypothesis will be tested at a 5% level of significance. Testing will be done using a Cochran-Mantel-Haenszel (CMH) test with biologic/JAK inhibitor prior use status ('Yes' vs 'No'), baseline corticosteroid use ('Yes' vs 'No'), and baseline disease activity ('Low' vs 'High') as the stratification factors. The stratification factors will be treated as-randomized regardless of actual participant stratification. The CMH chi-square p -value, stratified risk difference ("common" risk difference) with 95% CI using the Newcombe method, Mantel-Haenszel odds ratio, and 95% CI for the Mantel-Haenszel odds ratio will be reported for pairwise comparisons between VTX002 60 mg and placebo, along with number and percentage of participants in clinical remission in each as-randomized treatment group.

The following SAS pseudo-code will be used for computation of Cochran-Mantel-Haenszel 'general association' p -values (based on table scores), exact odds ratios and confidence intervals, and Newcombe common risk differences in the presence of randomization stratification factors:

```
[REDACTED SAS PSEUDO-CODE]
```

Additionally, unstratified common risk differences will be generated and presented along with the Mantel-Fleiss criterion ([Mantel 1980](#)):

```
[REDACTED SAS PSEUDO-CODE]
```

In all cases, statistical analyses accounting for randomization stratification factors will be considered primary.

Additional adhoc analysis methods may be employed subsequent to the Induction Period Analysis database lock and unblinding if the presence of zeroes in 2x2 responder frequency tables (one for each stratum, see [Section 10.2](#)) creates difficulties for implementation of the pre-specified analysis approach.

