5. PLANNED ANALYSES

Each planned analysis identified in this SAP will be performed after

- SAP is authorized by the study sponsor
- Database lock is completed as appropriate for the given planned analysis
- Study treatment is unblinded (if necessary) as appropriate for the given planned analysis

Any post hoc exploratory analyses completed to support planned study analyses not identified in this SAP will be documented and reported in the Clinical Study Report (CSR). Any results from these unplanned analyses will be clearly identified in the text of the CSR.

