10.2 Randomization Stratification

For the Induction Treatment Period, all participants are randomized to study treatment using permuted block randomization with block sizes of six, as specified in the Randomization

Specification Form (28 July 2021). This will be done via a IWRS. Under version 1.0 of the Protocol, the stratification factors were the following:

- biologic/JAK inhibitor *failed* status (yes/no)
- baseline corticosteroid use (yes/no)
- baseline disease activity (MMS 4-6 or 7-9)

Under subsequent Protocol versions the stratification factors are the following:

- biologic/JAK inhibitor prior use status (yes/no)
- baseline corticosteroid use (yes/no)
- baseline disease activity (MMS 5-6 or 7-9)

The randomization list was not updated to reflect these changes, and the IWRS system was kept as-is (Randomization Plan, version 2.0; 25 July 2022). For most statistical analysis purposes the following will be used:

- biologic/JAK inhibitor prior use status (yes/no)
- baseline corticosteroid use (yes/no)
- baseline disease activity (MMS 5-6 or 7-9) (i.e., participants with MMS of 4 at baseline according to IWRS are excluded from most efficacy analyses; however, see [Sections 10.5](#) and [16.1.5](#) for several analyses that include them)

In all cases, randomized stratum will be used in the primary analysis of primary and key secondary efficacy analyses. A sensitivity analysis of the primary analysis of the primary endpoint will be generated using actual stratum as collected in EDC. Descriptive statistics based on actual stratum will be generated. See [Section 16.1.7](#).

Data will be pooled across geographic region, country, and investigational site. No adjustment for these factors will be included in any statistical analysis.

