16.2 Key Secondary Analyses

Key secondary efficacy endpoints are defined in [Section 7.2](#):

- Hypothesis testing of these endpoints for VTX002 60 mg versus placebo are considered key secondary analyses
- Hypothesis testing of the primary efficacy endpoint for VTX002 30 mg versus placebo, in addition to hypothesis testing of the key secondary efficacy endpoints for VTX002 30 mg versus placebo, are also considered key secondary analyses

The primary analyses of these hypothesis tests are subject to the family-wise Type 1 error rate handling and gatekeeping (i.e., multiplicity adjustments) described in [Section 10.3](#). After attribution of known outcome at Induction Week 13 (see introduction to [Section 16](#)), the primary planned Key Secondary Analyses as described [Table 6](#) will be conducted.

The CMH methodology used for the primary analysis of the primary endpoint will be used for all Key Secondary Analyses. The additional primary endpoint analysis methods described in [Sections 16.1.4](#) and [16.1.6](#) – missing data methods (MAR multiple imputation, copy reference multiple imputation, tipping point), randomization stratification factor (EDC) sensitivity analysis, and supplementary analyses (application of mFAS and PP analysis sets to primary analysis methods) – will also be applied to the Key Secondary endpoints. See [Table 6](#).

For tipping point analyses, identification of participants not contributing observed data at Visit 7 Week 13 will rely on the types of data needed for a given Key Secondary endpoint. For example, endoscopic improvement-histologic remission (the fourth Key Secondary endpoint) requires Geboes and ES to both be available. If they are not available for a given participant, that participant will be subject to tipping point analysis. The set of participants subject to tipping point analysis may differ from one endpoint to another.

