Table 6. Planned Primary and Key Secondary Analyses

X = VTX002 60 mg vs Placebo

Y = VTX002 30 mg vs Placebo

Endpoint	Primary Analysis with Stratified CMH (FAS)	Key Secondary Analyses with Stratified CMH ^b (FAS)	Section 16.1.4 Missing Data Sensitivity Analyses (FAS: MAR MI, CR MI, Tipping Point)	Section 16.1.5 Sensitivity Analysis (FAS)	Section 16.1.6 Supplementary Analyses (mFAS, PP Sets)	Section 16.1.7 Sensitivity Analyses (FAS)
Primary endpoint – Clinical Remission	X ^a Family 1	Y Family 4	X, Y	X	X, Y	X, Y
Key Secondary Endpoints						
Endoscopic Improvement		X: Family 2 Y: Family 5	X, Y		X, Y	X, Y
Symptomatic Remission		X: Family 2 Y: Family 5	X, Y		X, Y	X, Y
Histologic Remission		X: Family 3 Y: Family 6	X, Y		X, Y	X, Y
Endoscopic improvement – Histologic Remission		X: Family 3 Y: Family 6	X, Y		X, Y	X, Y

^a Serves as primary analysis gatekeeper for testing all Key Secondary Analyses with Stratified CMH

^b The collection of Key Secondary Analyses with Stratified CMH subject to a truncated Hochberg multiplicity adjustment to control the family-wise Type 1 error rate at $\alpha=0.05$. [Figure 3, Section 10.3](#) presents a flow chart demonstrating how this is to be done.

CMH = Cochran-Mantel-Haenszel; CR = copy reference; FAS = Full Analysis Set; mFAS = modified Full Analysis Set; PP = Per Protocol set; MI = multiple imputation; MAR = missing at random

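### Does the SAP's allowance for ad hoc methods after unblinding put the primary CMH p-value and its 5% level at risk?

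*SAP*

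**What the plan says.** SAP 16.1.3 tests clinical remission at Week 13, 60 mg against placebo, with a CMH test stratified by three binary as-randomised factors. "The null hypothesis will be tested at a 5% level of significance". Protocol 9.4.1.1 names the same test. After adding unstratified risk differences and the Mantel-Fleiss criterion, SAP 16.1.3 states: "In all cases, statistical analyses accounting for randomization stratification factors will be considered primary". The next paragraph reads "Additional adhoc analysis methods may be employed subsequent to the Induction Period Analysis database lock and unblinding", on the condition that zeroes in the per-stratum 2x2 tables are such that their presence "creates difficulties for implementation of the pre-specified analysis approach".

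Three other places bear on this:

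- SAP 16.2 extends the test: "The CMH methodology used for the primary analysis of the primary endpoint will be used for all Key Secondary Analyses".
- SAP Table 6 places the primary comparison in a column headed by the stratified CMH on the FAS, as Family 1. Its footnote a says: "Serves as primary analysis gatekeeper for testing all Key Secondary Analyses with Stratified CMH".
- SAP 5 describes unplanned work as post hoc, exploratory and done in support of the planned analyses, and adds: "Any results from these unplanned analyses will be clearly identified in the text of the CSR". SAP 10.4 leaves every test outside the six families uncontrolled.

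**The concern.** The clause has the marks of a weak pre-specification. The choice is made after unblinding, no method is listed, and the only limit is an undefined word, *difficulties*. The sentence that keeps stratified analyses primary rules out an unstratified replacement but does not say which stratified analysis counts. Merged strata, an adjusted logistic model, a stratified risk-difference test and an exact test all account for the factors. If one of these could stand in for the CMH p-value, the 5% level would rest on a choice made with the results in view. The primary test opens the gate to the other nine of the ten controlled tests (10 - 1 = 9), so any inflation would carry forward.

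**Working it through.** **Inputs.** Rates of 28% and 8%, two-sided 5%, 57 per group raised to 63: SAP 6 and Appendix VII. Strata: 2 x 2 x 2 = 8 (SAP 16.1.3). Randomisation: "permuted block randomization with block sizes of six" (SAP 10.2). Stratum shares: SAP 4.1 gives only about 35% with inadequate response to biologics, used here as a proxy for prior use. The other shares are assumptions: corticosteroid use 25% to 50% and MMS 7-9 50% to 70%. Remission rates are taken as equal across strata.

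**1. The plan's own figure.** n = [1.960 x sqrt(2 x 0.18 x 0.82) + 0.8416 x sqrt(0.08 x 0.92 + 0.28 x 0.72)]^2 / 0.20^2 = (1.0649 + 0.4415)^2 / 0.04 = 56.7, so 57. Power at 57 is 0.802. Both match Appendix VII.

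**2. Are zero cells likely?** Yes. Expected placebo remitters are 63 x 0.08 = 5.04, spread over eight strata, so several strata will usually have none. The condition on zero cells is therefore met in almost every trial, and only the word *difficulties* limits the clause.

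**3. Do zero cells stop the CMH test?** The statistic is (sum of a - E)^2 / (sum of V), with V = n1 n0 r (N - r) / [N^2 (N - 1)] in each stratum, where r is the number of remitters. A stratum with a zero cell still contributes as long as it holds both arms and has both remitters and non-remitters. The test fails only if every stratum has V = 0. In practice that means no remitters at all:

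- both arms at 8%: 0.92^126 = 0.000027, or 0.003%
- 28% vs 8%: 0.92^63 x 0.72^63 = 0.0052 x 0.000000001, effectively zero

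**4. Simulation** (200,000 trials per scenario, 63 per arm, near-equal arms within strata; ranges over the assumed shares):

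| | 28% vs 8% | both 8% | both 18% |
|---|---|---|---|
| At least one zero cell | over 99.9% | 100% | 99.2% to 99.98% |
| Mean strata with a zero cell | 4.6 to 5.0 | 6.1 to 6.2 | 3.3 to 4.1 |
| CMH undefined | 0 | 0.002% to 0.003% | 0 |
| CMH rejects | 85.4% to 85.7% | 4.8% | 4.9% to 5.0% |

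Separate runs with blocks of six within strata gave CMH undefined in at most 0.005% and type I error of 4.7% to 5.0%.

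**5. Effect on the gate.** If another test were used only where the CMH cannot be computed, the chance of wrongly opening the gate is at most P(CMH rejects) + P(CMH undefined) = 5.0% + 0.005% = 5.005%.

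**6. Where difficulties can arise.** They arise in the estimates. The Mantel-Haenszel odds ratio is infinite when placebo has no remitters: 0.92^63 = 0.5%. With both arms at 8% it is zero or infinite in about 1.1% of trials. A stratum has one arm empty in about 5% of trials (0% to 62% over the assumed shares). SAP 16.1.3 already lists exact odds ratios with confidence intervals and unstratified risk differences.

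**The case for a change.** The strongest contrary reading is that the condition concerns implementing the pre-specified approach, which is just when an analyst would look for a substitute. SAP 5 requires disclosure but does not forbid replacement. SAP 10.4 speaks of tests described in the SAP, and an unnamed method is not described there. The Mantel-Fleiss criterion is reported with no rule attached, and it would fall below 5 in 57% of trials with both arms at 8%, which could be offered as a reason to switch.

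An inflation can also be calculated. Taking the smallest p-value among the eight-stratum CMH and three CMH tests on collapsed strata gives 5.2% to 5.3%. Taking it over four stratum-adjusted tests, one of them a main-effects logistic likelihood-ratio test, gives 6.3% to 6.6% with both arms at 8%.

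It is true that no single sentence says outright that the CMH p-value cannot be displaced. The inflation figures do not measure this clause, however. They select the smallest p-value in every trial, whether or not the CMH could be computed. The larger figure comes mainly from the logistic test, which rejects 6.0% to 6.5% of the time on its own with both arms at 8%; pairing it with the CMH leaves that range unchanged. The low Mantel-Fleiss values give no reason to switch either, because the CMH test holds its level in the same trials (4.8%).

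**Conclusion.** No change is needed. The clause is missing detail that an analyst would fill sensibly: compute the stratified CMH, which is available in essentially every trial, report it as the Family 1 result, and present anything else as supportive. The word additional, the sentence keeping stratified analyses primary, SAP 5, SAP 10.4 and Table 6 all point the same way. The primary test, its strata, its level and its place as gatekeeper are all fixed. The same holds for the key secondary tests, which use the same method.

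The exposure on the primary p-value is at most about 0.005 percentage points, confined to trials with almost no remitters in either arm. A rule that fixed the CMH p-value and named an exact stratified test for the undefined case would return p = 1 there, so it would change no decision. One sentence saying that ad hoc methods cannot open Families 2 to 6 would do no harm, but the result would be the same.

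This rests on assumed stratum shares (only the 35% has a source in the documents), equal remission rates across strata, and 63 analysed per arm. The conclusion did not move over the ranges tried.
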